6.3 Modalities of recruitment

6.3.1 Dentist selection

To gather a nationwide number of resident dentists, the expected number of sites is ca. 100 of practicing dentists working in private practices throughout Germany.

6.3.2 Patient selection

Each selected dentist and who will have agreed to participate to the study should have included up to 6 patients who meet inclusion criteria (treatment with OraVerse® within the last 3 months before contract signing).

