- to record retrospective data coming from the charts of eligible patients (latest consecutive administrations of OraVerse® within the last 3 months up to a maximum of 6 patients) including patient age, classification of body weight, type of dental intervention, name and dose of the product for anaesthetic procedure, dose of OraVerse®

Information will be obtained anonymously directly from patients files by dentists retrospectively.

Statistical methodology

Descriptive statistics for all collected and derived data will be provided. For continuous data number of patients, mean, standard deviation, median, min, max, quartiles and appropriate other percentiles will be provided. For categorical data frequencies and percentages will be presented. For estimated parameters suitable 95 % confidence intervals will be provided.

Statistical power and sample size justification:

With a sample size of 500 patients the following statistical precision for the estimated proportion of patients who 'not comply'/'comply' with the doses and indications recommended in the SmPC can be reached: Assuming rates of not adherence/adherence to labelling of 3%/97% or 4%/96% or 5%/95%, the 2-sided 95% confidence intervals will be [1.5%; 4.5%]/[95.5%; 98.5%] or [2.3%; 5.7%]/[94.3%; 97.7%] or [3.1%; 6.9%]/[93.1%; 96.9%].

In general: when the sample size is 500, a two-sided 95.0% confidence interval for a single proportion using the large sample normal approximation will extend 0.015 or 0.017 or 0.019 from the observed proportion for an expected proportion of 0.030 (or 0.97) or 0.04 (or 0.96) or 0.05 (or 0.95).

Timelines

Protocol planned date: February 2014

Database lock planned date: 31 July 2014

Duration of retrospective survey/data collection: planned May - June 2014

Estimated Report date: January 2015

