4. STUDY OBJECTIVES

Primary objectives:

To investigate the conditions of use of OraVerse® after local anaesthetic procedure in daily routine. The documentation will include the following points:

total number of patients treated with OraVerse® within the previous 3 months

latest consecutive administrations of OraVerse® within the last 3 months up to a maximum of 6 patients before contract signing:

- patient age,
- classification of body weight
- type of dental intervention,
- local anesthetic used (product and dose),
- dose of OraVerse® used

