5. STUDY DESIGN

5.1 Description of the study design

This drug utilization survey is described in the RISK MANAGEMENT PLAN (RMP) of OraVerse® and was requested during the European approval procedure. It will provide further information about the conditions of use of OraVerse® in routine clinical practice (i.e. patient age, type of dental intervention, local anesthetic used (product and dose) and dose of OraVerse®) used in patients normally treated with OraVerse® after local anesthetic procedure by dentists. It also provides information about use for orofacial procedures other than routine dental procedures, use in children < 6 years or use in patients undergoing complex dental procedures, i.e. for indications different from those described in the SmPC.

The only way to monitor the use of the product will be to collect information directly from dentists. In order to limit intervention bias, a retrospective (retrolective) design will be used to evaluate patients already treated with OraVerse[®].

As OraVerse® is planned to be used by dentists in the frame of dental interventions and will not be reimbursed, it will not be recorded in any national databases/registers in the countries where it will be used. So, the collection of information on patients profile and characteristics of dental intervention will need to be made at dentists' level.

Data documentation will happen after signing the contract:

In order to limit intervention bias, a retrospective design will be used to collect data of the latest
consecutive administrations of OraVerse® within the last 3 months up to a maximum of 6 patients
after signing the contract.

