8.2 Logistic aspects

Each of the participating dental centres and each of the dentists will be provided by Sanofi a file containing:

- NIS contract
- Protocol of the study
- Overview-page

- Facsimile
- For each documented patient (n=6)
 - CRF
- OraVerse® SmPC

The documents (CRF, overview-page) will be collected at dentist practice level and send in the enclosed envelope by mail to the CRO (Important: without name or address of the sender).

The enclosed Facsimile (containing number of documented patients (max 6), date, name, signature and personal seal of the dentist) will be faxed to NIS Management of Sanofi-Aventis Deutschland GmbH to [name] (No: [contact]).

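### Section 6.3.2 omits the consecutive-case rule, and the look-back window closes at contract signing rather than before the dentist receives the study material

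*Protocol*

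**What the plan says.** Three places in the protocol give an order rule for choosing cases. The synopsis (main data collected) asks for "latest consecutive administrations of OraVerse® within the last 3 months up to a maximum of 6 patients". Section 4 has the same rule and adds the time anchor: "latest consecutive administrations of OraVerse® within the last 3 months up to a maximum of 6 patients before contract signing". Section 5.1 also asks for the latest "consecutive administrations of OraVerse® within the last 3 months up to a maximum of 6 patients", and closes that sentence with "after signing the contract".

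Section 6.3.2, which is headed as the patient selection section, says only that each participating dentist "should have included up to 6 patients who meet inclusion criteria (treatment with OraVerse® within the last 3 months before contract signing". It contains neither an order nor a consecutiveness requirement. Sections 6.2.1, 7 and 11.1 define the same three-month window before signing, also without an order rule.

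Section 5.1 gives the reason for looking backwards: "In order to limit intervention bias, a retrospective design will be used to collect data of the latest" cases.

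Section 8.2 describes what the dentist receives: "Each of the participating dental centres and each of the dentists will be provided by Sanofi a file containing" the contract, the protocol, an overview page, a fax form, the CRFs and the SmPC. Section 9.2 states that quality control at the sites is impossible because the survey is anonymous. Section 13.3 states that CRFs carry no patient or site number and cannot be traced back.

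**The concern.** The primary outcome (section 11.2.1) is the proportion of patients treated in line with the SmPC. The person who selects the cases is the person whose practice is being described, so the result depends on a selection rule that leaves the dentist no discretion and on cases that predate awareness of the survey. Two features weaken this.

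1. **Which cases.** The section a dentist would naturally consult for selection lacks the consecutive rule. A dentist with more than six eligible patients could follow 6.3.2 to the letter and still choose among them.
2. **Which period.** The window closes at an act of the dentist, signing the contract. No section sets an index date before the dentist is contacted or receives the file. Cases treated between receipt and signing would count, and a latest-first rule ranks them at the top.

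Both work against the stated aim of limiting intervention bias. Neither could be repaired at analysis, because skipped cases leave no trace in the data.

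**Working it through.** **Step 1: the selection rule, section by section**

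| Place | Latest consecutive? | Time anchor for treatment |
|---|---|---|
| Synopsis, main data collected | Yes | Last 3 months, signing not mentioned |
| Section 4 | Yes | Before signing |
| Section 5.1 | Yes | Last 3 months; the sentence ends with a reference to after signing |
| Section 6.2.1 | No | Before signing |
| Section 6.3.2 | No | Before signing |
| Section 7 | No | Before signing |
| Section 11.1 | No | Before signing |

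The rule therefore exists, but it is missing from the section that governs selection.

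**Step 2: could a departure be seen afterwards?** The items listed for collection (synopsis, sections 4 and 8.1) do not include a treatment date. The total number of patients treated in the three months is requested, which shows whether a dentist had a choice but not which cases were taken. Sections 9.2 and 13.3 exclude site checks and tracing. The written rule is the only safeguard.

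**Step 3: the protocol's own precision.** Inputs from section 11.4: n = 500, rates 3%, 4% and 5%, two-sided 95%, normal approximation. Half-width = 1.96 × √(p(1−p)/500).

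- p = 0.03: 0.0150, interval 1.5% to 4.5%
- p = 0.04: 0.0172, interval 2.3% to 5.7%
- p = 0.05: 0.0191, interval 3.1% to 6.9%

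All three match the protocol. They describe sampling error only.

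**Step 4: what selective omission would do (illustration).** Let p be the true non-compliance and s the share of non-compliant cases passed over. The documents give no value for s, so a range is shown. The expected observed rate is

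q = p(1−s) / [p(1−s) + (1−p)].

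For p = 0.05:

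- s = 10%: 0.045/0.995 = 4.5%
- s = 25%: 0.0375/0.9875 = 3.8%
- s = 50%: 0.025/0.975 = 2.6%

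The chance that the planned interval contains the true p, summed over Binomial(500, q):

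| True p | s = 0 | s = 10% | s = 25% | s = 50% |
|---|---|---|---|---|
| 3% | 92% | 87% | 70% | 24% |
| 4% | 93% | 86% | 65% | 15% |
| 5% | 93% | 86% | 62% | 10% |

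The s = 0 column shows that the normal approximation itself falls slightly below 95% here, so only the drop from that column is due to omission. The bias equals the planned half-width at s of about 40% (p = 5%), 44% (p = 4%) and 51% (p = 3%).

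This models omission only. It does not quantify changed practice between receiving the file and signing, for which the documents give nothing to calculate with.

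**The case against.** **Section 6.3.2 is silent, not permissive.** Each dentist receives the whole protocol (section 8.2) and must collect data in line with it (section 12.2). Read together, the sections still require consecutive cases. This stands: it would be too strong to say that the protocol grants free choice. What remains is that a reader of 6.3.2 alone would not know of the rule.

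**Section 5.1 does not open a second window.** A reader might infer from "after signing the contract" that patients treated after signing are to be included, against section 4. The lead-in to that bullet is "Data documentation will happen after signing the contract", so the phrase most naturally dates the recording of data. The synopsis and sections 4, 6.2.1, 6.3.2, 7 and 11.1 all place treatment before signing. This is awkward word order, not a contradictory eligibility period.

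**The order of receipt and signing is not stated.** Section 8.2 lists the contract in the file but does not say whether it is sent for signature or as a copy of one already signed. This stands, and the second part of the concern is conditional on it.

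**Opportunity is not evidence.** A reader might infer that dentists will choose favourable cases or change their practice. Nothing in the document shows either. Downward bias is plausible but not derived, and small amounts of omission do limited harm: at a true 5%, s = 10% moves the expected rate by about 0.5 percentage points against a half-width of 1.9.

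**Conclusion.** The point holds as a gap in the selection rule and a weak choice of anchor date. The consecutive-case requirement is absent from section 6.3.2. Nothing in the protocol fixes the window before the dentist has seen the survey questions and the standard applied. Since a departure could not be detected, the wording carries the whole burden.

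The first part rests on the text alone. The second rests on the inference that signing follows receipt of the file. The size of any bias cannot be derived from the documents: the fall from 5% to between 4.5% and 2.6% is conditional on an assumed omission rate of 10% to 50% and is not a forecast. No figure in the sample size section is wrong. This is an inexpensive improvement that should be made, not a flaw that invalidates the survey.

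**What to change.** Use one rule, worded identically in the synopsis and sections 4, 5.1, 6.2.1 and 6.3.2: the most recent consecutive patients treated with OraVerse, at most six and none skipped, in the three months before a fixed index date. Set that date before the dentist receives any study material and print it on the overview page. In section 5.1, move the reference to signing so that it clearly describes when data are documented, not when patients were treated.

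The cost is wording in the protocol and on the overview page; sample size and analysis are unchanged. The most recent cases before signing fall outside the window. The number lost cannot be estimated from the document, and recruitment has moderate slack: about 100 sites × 6 = 600 places for 526 planned patients, or about 5.3 per site. Whether cases were skipped remains unverifiable under anonymous CRFs, so the study report should state this as a limitation.

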1. SYNOPSIS

COMPOUND: OraVerse®

STUDY NO.: PHENLL07113

Title	Actual conditions of use of OraVerse® in patients among resident dentists throughout Germany
Location	Germany
Objectives	To investigate the conditions of use of OraVerse® after local anesthetic procedure in daily routine practice. The primary outcome will be the incidence of patients who "comply"/"not comply" with the recommendations in the SmPC regarding the following points: • patient age, • classification of body weight • type of dental intervention, • local anesthetic used (product and dose), • dose of OraVerse® used
Population	 Inclusion Criteria Patients treated with OraVerse® after treatment with a local anesthetic containing a vasoconstrictor (such as epinephrine) by dentists within the last 3 months before contract signing Expected number of patients: 526 (500 evaluable) Sample Size: 500 treated (evaluable) patients assuming a 5% non-evaluable rate. Expected number of sites: ca. 100 To gather a nationwide number of resident dentists
Population	 Inclusion Criteria Patients treated with OraVerse® after local anesthetic procedure by dentists within the last 3 months before contract signing Expected number of patients: 526 (500 evaluable) Sample Size: 500 treated (evaluable) patients assuming a 5% non-evaluable rate. Expected number of sites: ca. 100 To gather a nationwide number of resident dentists

Recruitment modalities

Retrospective cross-sectional drug utilisation survey among resident dentists throughout Germany

- Eligible patients:
 - All patients normally treated with OraVerse® after local anesthetic procedure by dentists within the last 3 months before contract signing
- Participating dentists:
 - must be practicing dentists working in private practices,
 - must be dentists performing routine dental interventions using local anesthetic procedure,
 - must have used OraVerse® in the 3 previous months.

Main evaluation criteria

• Primary outcomes:

The outcomes of interest will be the conditions of use of treatment. The primary outcomes will be the incidence of patients who "comply"/"not comply" with the recommendations in the SmPC regarding the following points:

- patient age,
- classification of body weight
- type of dental intervention,
- local anesthetic used (product and dose),
- dose of OraVerse[®] used

Main data collected

Dentists will be asked

- to indicate total number of patients normally treated with OraVerse® within the previous 3 months,

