13.3 Data protection

As defined and described in the RISK MANAGEMENT PLAN for Oraverse®, data collection will be completely anonymous. No backtracking will be possible, since the CRFs will be documented and evaluated without any identification attribute (no patient number, no site number). Therefore no informed consent of the patient is necessary.

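### The selection rule caps each dentist at 6 patients but never requires the series to be complete, and this protocol compares none of the counts it collects

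*Protocol*

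**What the plan says.** Section 6.3.2, the section that governs patient selection, says that each participating dentist "should have included up to 6 patients who meet inclusion criteria". It gives no order and no minimum. The synopsis supplies an order: "latest consecutive administrations of OraVerse® within the last 3 months up to a maximum of 6 patients". Section 4 repeats it ("latest consecutive administrations of OraVerse® within the last 3 months up to a maximum of 6 patients before contract signing"), and section 5.1 has similar wording. None of these places says that documentation continues until six cases are reached or the window is exhausted.

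Three counts arise in the survey:

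- The dentist is asked "to indicate total number of patients normally treated with OraVerse® within the previous 3 months" (synopsis; also section 4).
- A facsimile goes to the sponsor, "containing number of documented patients (max 6), date, name, signature and personal seal of the dentist" (section 8.2).
- The CRFs and overview-page go to the CRO in an envelope that does not identify the sender (section 8.2), so the CRFs received can be counted there.

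Under section 13.3, "CRFs will be documented and evaluated without any identification attribute (no patient number, no site number" applies. Section 9.2 states that quality control at site level is not possible. Section 9.1 leaves collection and validation procedures to a Data Management Plan that is not shown. The protocol itself describes no comparison of the three counts.

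**The concern.** An order of selection fixes which case comes next. It does not fix where the series ends. The person who decides where it ends is the dentist whose adherence to the label is being measured. That dentist works from existing charts and has the SmPC in the same file as the CRFs (section 8.2). Someone with ten eligible patients who documents the latest two, or who stops just before an off-label case, has broken no written rule.

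The primary outcome is the proportion not complying with the SmPC, planned around 3% to 5%. At that level, a few non-compliant cases left out change the estimate noticeably, and always towards better compliance. The survey was requested in the European approval procedure (section 3.2), so a favourable bias matters. The rule given to dentists cannot be changed once they have filled in their CRFs. Because the CRFs carry no site number, a dentist's CRFs can be set against that dentist's own total only while they are still together in one envelope.

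**Working it through.** **1. The plan's own precision.** Section 11.4 uses n = 500 and non-compliance p of 3%, 4% and 5%. The half-width is 1.96 × √(p(1 − p)/500):

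- p = 3%: 0.0150
- p = 4%: 0.0172
- p = 5%: 0.0191

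These match the stated 0.015, 0.017 and 0.019.

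**2. Bias if some dentists stop before their first off-label case.** The documents give no share of such dentists, so s = 10%, 30% and 50% are assumptions. The model also assumes that every dentist has at least six eligible patients and that each case is non-compliant independently with the same probability p.

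A dentist who does not stop early returns 6 CRFs, of which 6p are non-compliant on average. A dentist who stops early returns only the run before the first off-label case, with expected length E = Σ(1 − p)^k for k = 1 to 6, all compliant:

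- p = 5%: E = 0.950 + 0.903 + 0.857 + 0.815 + 0.774 + 0.735 = 5.03
- p = 3%: E = 5.40

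Observed rate = (1 − s)·6p / [(1 − s)·6 + s·E].

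| True p | s = 10% | s = 30% | s = 50% |
|---|---|---|---|
| 5% | 0.270/5.903 = 4.57% | 0.210/5.710 = 3.68% | 0.150/5.517 = 2.72% |
| 3% | 0.162/5.940 = 2.73% | 0.126/5.820 = 2.16% | 0.090/5.700 = 1.58% |

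The shift is 0.3 to 0.4 points at s = 10%, well inside the stated half-widths of 1.5 to 1.9 points. At s = 30% to 50% it is 0.8 to 2.3 points, comparable with them.

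**3. Would the recruitment total show it?** With 100 dentists, p = 5% and s = 30%, the CRFs returned are 100 × 5.710 = 571 of 600. That is above the planned 526, so reaching the target is no evidence of complete series.

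**4. A second model as a cross-check.** Suppose 526 of 600 possible CRFs arrive, so a fraction f = 74/600 = 12.3% is omitted. Suppose also that non-compliant cases are omitted m times as often as compliant ones (m assumed). With q = f/(pm + 1 − p), the observed rate is p(1 − mq)/(1 − f).

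| True p | m = 1 | m = 2 | m = 3 | m = 5 |
|---|---|---|---|---|
| 5% | 5.0% | 4.4% | 3.8% | 2.8% |
| 3% | 3.0% | 2.6% | 2.2% | 1.5% |

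The understatement is 0.4 to 2.2 points for m = 2 to 5, the same order as in step 2. With m = 1, omission unrelated to compliance, there is no bias.

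**5. What the counts can show.** The total of the faxed counts against the CRFs received shows unreturned CRFs in aggregate. The number of CRFs in one envelope against min(6, 3-month total) shows a shortened series. The second comparison needs the 3-month total to be in that envelope. The protocol does not give the content of the overview-page, so this is an assumption.

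**The case against.** The natural reading of the synopsis and sections 4 and 5.1 is to work back from the latest case until six are documented or the three months run out, with the ceiling worded to allow for dentists who have fewer. Dentists receive the protocol and six CRFs. This stands in part: they are given an order as well as a maximum, and a reader who took 6.3.2 alone to be the whole instruction would be mistaken. But the order still carries no duty to finish, and 6.3.2 omits even the order.

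A reader might also infer that no count check exists, that a shortfall could never be detected, or that nothing could be done afterwards. The documents do not support this. Reconciliation of CRFs could be in the Data Management Plan. Unreturned CRFs can be seen in aggregate from counts already collected, and an operational instruction issued before data arrive could add a tally at envelope opening. What anonymity does rule out is recovering individual cases, or linking a CRF to a dentist after pooling, and sections 9.2 and 13.3 openly accept that no site-level control or backtracking is possible.

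Finally, every share and ratio in the calculation is assumed, the shift at a 10% share is small, and section 11.3 calls all analyses exploratory. That is correct, and it limits the claim to a possible bias of unknown size.

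**Conclusion.** The point holds as a weakness in a stated selection rule. No place in the protocol requires a dentist to continue to six cases or to the end of the window, and a series cut before an off-label case would overstate compliance without breaching any written instruction. Under assumed shares of 10% to 50% of dentists stopping early, a true 5% non-compliance would appear as 4.6% to 2.7%, and a true 3% as 2.7% to 1.6%. These figures rest on independent cases with a common rate and at least six eligible patients per dentist. They illustrate the possible effect; they do not estimate it, and nothing in the documents shows that selective stopping occurs.

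The absence of a count comparison can be stated of this protocol only. This is a cheap improvement, best made before dentists receive their instructions.

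**What to change.** 1. In section 6.3.2, the synopsis and sections 4 and 5.1, replace the ceiling with: *the latest 6 consecutive eligible patients, or all of them if fewer than 6 were treated in the window*. Ask for the 3-month total over the same window and for the same eligible patients.
2. At envelope opening, before pooling, have the CRO record the number of CRFs against min(6, 3-month total), without any identity. This assumes the total is on the overview-page in the same envelope; if it is not, add it there.
3. At close, compare the summed facsimile counts with the CRFs received, as totals only, so that anonymity is kept.
4. Report the shortfall and the return rate, with a worst-case bound that counts missing cases as not compliant: with x non-compliant among n received and d missing, (x + d)/(n + d). The shortfalls from steps 2 and 3 can overlap, so show them separately; adding them makes the bound conservative.

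The cost is one sentence in the protocol and the dentists' instructions, a tally at opening and one extra table. Some dentists would complete a few more short CRFs. No identifiers are needed, and no dentist exceeds the planned maximum of six.

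Two limits remain. The check does not detect an off-label case skipped and replaced by an older one, and it relies on a total reported by the same dentist.
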